### 11.9.6. Pharmacokinetic Tables

Pharmacokinetic: Tables					
No.	Population	GSK Standard / Example Shell	Title	Programming Notes	Deliverable [Priority]
Pharmacokinetic Parameters					
4.1.	PK Parameter	PK_01	Summary of Derived Plasma Cabotegravir PK Parameters by Study Phase		Interim, SAC
4.2.	PK Parameter	PK_01	Summary of Derived Plasma Rilpivirine PK Parameters by Study Phase		Interim, SAC
Pharmacokinetic Concentration					
4.3.	PK Concentration	PK01	Summary of Plasma Cabotegravir PK Concentration (ug/mL)-Time Data by Study Phase and Nominal Timepoint		SAC
4.4.	PK Concentration	PK01	Summary of Plasma Rilpivirine PK Concentration (ng/mL)-Time Data by Study Phase and Nominal Timepoint		SAC

### 11.9.7. Pharmacokinetic Figures

Pharmacokinetic: Figures					
No.	Population	GSK Standard / Example Shell	Title	Programming Notes	Deliverable [Priority]
Pharmacokinetic Mean/Median Plots					
4.5.	PK Parameter	PK17	Mean (SD) Plasma Cabotegravir Concentration-Time Plots (Linear and Semi-Log) by Study Phase	Display oral and LA phases on separate pages	SAC
4.6.	PK Parameter	PK17	Mean (SD) Plasma Rilpivirine Concentration-Time Plots (Linear and Semi-Log) by Study Phase	Display oral and LA phases on separate pages	SAC
4.7.	PK Parameter	PK20	Median (5 th and 95 th Percentile) Plasma Cabotegravir Concentration-Time Plots (Linear and Semi-Log) by Study Phase	Display oral and LA phases on separate pages	SAC
4.8.	PK Parameter	PK20	Median (5 th and 95 th Percentile) Plasma Rilpivirine Concentration-Time Plots (Linear and Semi-Log) by Study Phase	Display oral and LA phases on separate pages	SAC
Pharmacokinetic Individual Subject Plots					
4.9.	PK Parameter	PK16a	Individual Plasma Cabotegravir Concentration-Time Plots (Linear and Semi-Log) by Study Phase	Display oral and LA phases on separate pages	SAC
4.10.	PK Parameter	PK16a	Individual Plasma Rilpivirine Concentration-Time Plots (Linear and Semi-Log) by Study Phase	Display oral and LA phases on separate pages	SAC

### 11.9.8. Health Outcomes Tables

Health Outcomes Tables					
No.	Population	GSK Standard/ Example Shell	Title	Programming Notes	Deliverable [Priority]
Questionnaire Outcomes					
6.1.	Safety	201584/primary_07/T6.2	CCI		SAC
6.2.	Safety	201584/primary_07/T6.1			SAC
6.3.	Safety	201584/primary_07/T6.35			SAC
6.4.	Safety	201584/primary_07/T6.36			SAC
6.5.	Safety	201584/primary_07/T6.37			SAC
6.6.	Safety	201584/primary_07/T6.38			SAC
6.7.	Safety	201584/primary_07/T6.39			SAC

### 11.9.9. ICH Listings

ICH: Listings					
No.	Population	GSK Standard / Example Shell	Title	Programming Notes	Deliverable [Priority]
Subject Disposition					
1.	Screened	ES2	Listing of Reasons for Study Withdrawal	ICH E3	SAC
2.	Screened	SD2	Listing of Reasons for Study Treatment Discontinuation	ICH E3	SAC
Protocol Deviations					
3.	Screened	DV2	Listing of Protocol Deviations	ICH E3 Note: Include flag for important deviations (Y/N) and Covid-19 relatedness (Y/N)	SAC
4.	Screened	IE3	Listing of Subjects with Inclusion/Exclusion Criteria Deviations	ICH E3	SAC
Populations Analysed					
5.	Screened	SP3	Listing of Subjects Excluded from Any Population	ICH E3	SAC
Demographic and Baseline Characteristics					
6.	Screened	DM2	Listing of Demographic Characteristics	ICH E3 Include column indicating inclusion in the enrolled (Y/N) and safety populations (Y/N)	SAC
7.	Screened	DM9	Listing of Race	ICH E3 Include column indicating inclusion in the enrolled (Y/N) and safety populations (Y/N)	SAC
Exposure and Treatment Compliance					
8.	Screened	EX3	Listing of Exposure Data	ICH E3	SAC

## CONFIDENTIAL

208832

Adverse Events					
9.	Screened	AECP	Listing of All Adverse Events	ICH E3 Include column indicating Phase	SAC
10.	Screened	AE7	Listing of Subject Numbers for Individual Adverse Events	ICH E3 Replace the column for treatment with Phase	SAC
11.	Screened	AECP	Listing of Serious Adverse Events	ICH E3 Include column indicating Phase Note: Include Fatal vs Non-Fatal Designation	SAC
12.	Screened	AE14	Listing of Reasons for Considering as a Serious Adverse Event	ICH E3	SAC
13.	Screened	AECP	Listing of Adverse Events Leading to Withdrawal from Study or Permanent Discontinuation of Study Treatment	ICH E3 Include column indicating Phase	SAC
14.	Screened	AECP	Listing of Covid-19 Adverse Events	ICH E3 Include column indicating Phase Note: Display Covid-19 Adverse events and descriptive details	SAC
15.	Screened	PAN12	Listing of COVID-19 Assessments and Symptom Assessments		SAC
16.	Screened	PAN5	Listing of Dates of COVID-19 Pandemic Measures	Include Pandemic End date if available	SAC
All Laboratory					
17.	Screened	LB5	Listing of Continuous Laboratory Data by Lab Category, Study Phase, and Visit	ICH E3 Note: Include Chemistry and Hematology results	SAC
18.	Screened	LB14	Listing of Categorical Laboratory Data by Lab Category, Study Phase, and Visit	ICH E3 Note: Include Urinalysis, Coagulation, Drugs, and Infectious Disease results	SAC
19.	Screened	EG3	Listing of ECG Values by Study Phase and Visit	Sort by Phase and Visit	SAC
20.	Screened	EG5	Listing of ECG Findings by Study Phase and Visit	Sort by Phase and Visit	SAC
21.	Screened	VS4	Listing of Vital Signs by Study Phase and Visit	Sort by Phase and Visit	SAC

**CONFIDENTIAL**

208832

22.	Screened	PREG1	Listing of Subjects Who Became Pregnant During the Study		SAC
PK					
23.	Screened	PK07	Listing of Plasma Cabotegravir PK Concentration-Time Data by study phase		SAC
24.	Screened	PK07	Listing of Plasma Rilpivirine PK Concentration-Time Data by study phase		SAC

### 11.9.10. Non-ICH Listings

Non-ICH: Listings					
No.	Population	GSK Standard GSK Statistical Display Standard / Example Shell	Title	Programming Notes	Deliverable [Priority]
Subject Disposition					
25.	Screened	ES7	Listing of Reasons for Screen Failure	Journal Guidelines	SAC
26.	Screened	SD2	Listing of End of Study Record for Subjects Affected by Covid-19	Covid-19 relatedness as determined by Covid related AEs, PDs, missed visits, & Disposition	SAC
Prior and Concomitant Medications					
27.	Screened	MH2	Listing of Medical History for All Subjects		SAC
28.	Screened	CM3	Listing of Prior Medications	GSK Statistical Display Standard	SAC
29.	Screened	CM3	Listing of Concomitant Medications by Study Phase	GSK Statistical Display Standard	SAC
Adverse Events					
30.	Screened	AE8	Listing of Injection Site Reaction Adverse Events		SAC
31.	Screened	AE2	Listing of Relationship Between Adverse Event System Organ Classes, Preferred Terms, and Verbatim Text	GSK Statistical Display Standard	SAC
Laboratory Results					
32.	Screened	LIVER5	Listing of Liver Monitoring/Stopping Event Reporting	Note: See Appendix 11.4.4 for Criteria	SAC
33.	Screened	LIVER13	Listing Subjects Meeting Hepatobiliary Lab Abnormality Criteria	Note: See Appendix 11.4.4 for Criteria	SAC

## CONFIDENTIAL

208832

PK					
34.	Screened	PK13	Listing of Derived Plasma Cabotegravir PK Parameters by study phase		SAC
35.	Screened	PK13	Listing of Derived Plasma Rilpivirine PK Parameters by study phase		SAC
Health Outcome					
36.	Screened	HO_01	Listing of CCI Scores		SAC
37.	Screened	HO_02	Listing of CCI Questionnaire Results at Day 8		SAC
38.	Screened	HO_03	Listing of CCI from Daily Diary Cards		SAC

### 11.9.11. Mock Displays

Protocol: 208832

Page 1 of 1

Population: Safety

Table DISP\_T1  
Summary of Subject Disposition at Each Study Phase

Study Phase	Total (N=200)	
	ENTERED	xx (xx.x%)
Oral Lead-in Phase	COMPLETED	xx (xx.x%)
	WITHDRAWN	xx (xx.x%)
	COVID-19 RELATED[1]	xx (xx.x%)
Injection Phase	ENTERED	xx (xx.x%)
	COMPLETED	xx (xx.x%)
	WITHDRAWN	xx (xx.x%)
	COVID-19 RELATED[1]	xx (xx.x%)
Follow-up Phase	ENTERED	xx (xx.x%)
	COMPLETED	xx (xx.x%)
	WITHDRAWN	xx (xx.x%)
	COVID-19 RELATED[1]	xx (xx.x%)

[1] Covid-19 Related Disposition as collected from the Study Impact record

**CONFIDENTIAL**

208832

Protocol: 208832

Page 1 of 1

Population: Safety

Table DISP\_T2  
Summary of Reasons for Withdrawal at Each Study Phase

Primary Reason	Oral CAB 30mg + Oral RPV 25mg (N=100)	IM CAB 600mg + IM RPV 900mg - Injection Phase (N=100)	IM CAB 600mg + IM RPV 900mg - Follow-up Phase (N=100)	Overall (N=100)
ADVERSE EVENT	xx (xx.x%)	xx (xx.x%)	xx (xx.x%)	xx (xx.x%)
COVID-19 RELATED[1]	x (xx.x%)	x (xx.x%)	x (xx.x%)	x (xx.x%)
PROTOCOL DEVIATION	xx (xx.x%)	xx (xx.x%)	xx (xx.x%)	xx (xx.x%)
COVID-19 RELATED[1]	x (xx.x%)	x (xx.x%)	x (xx.x%)	x (xx.x%)
SUBJECT REACHED PROTOCOL-DEFINED STOPPING CRITERIA	xx (xx.x%)	xx (xx.x%)	xx (xx.x%)	xx (xx.x%)
STUDY TERMINATED BY SPONSOR	xx (xx.x%)	xx (xx.x%)	xx (xx.x%)	xx (xx.x%)
LOST TO FOLLOW-UP	xx (xx.x%)	xx (xx.x%)	xx (xx.x%)	xx (xx.x%)
INVESTIGATOR SITE CLOSED	xx (xx.x%)	xx (xx.x%)	xx (xx.x%)	xx (xx.x%)
PHYSICIAN DECISION	xx (xx.x%)	xx (xx.x%)	xx (xx.x%)	xx (xx.x%)
WITHDRAWAL BY SUBJECT	xx (xx.x%)	xx (xx.x%)	xx (xx.x%)	xx (xx.x%)
COVID-19 RELATED[1]	x (xx.x%)	x (xx.x%)	x (xx.x%)	x (xx.x%)

[1]

Covid-19 Related Disposition as collected from the Study Impact record

**CONFIDENTIAL**

208832

Protocol: 208832

Page 1 of x

Population: Pharmacokinetic Parameter

PK\_01

## Summary of Derived Cabotegravir Pharmacokinetic Parameters by Phase

Parameter	Summary Statistics	Oral CAB 30mg (N=xx)	IM CAB 600 mg (N=xx)
AUC 0-t (h* $\mu$ g/mL)	n	xx	xx
	Mean (SD)	XXX.X (xx.xx)	XXX.X (xx.xx)
	95% CI	(xxxx.xx, xxxx.xx)	(xxxx.xx, xxxx.xx)
	%CV	xx.x	xx.x
	Median	XXX.XX	XXX.XX
	Min, Max	XXX.X, XXX.X	XXX.X, XXX.X
	Geometric mean	XXX.XX	XXX.XX
	95% CI	(xxxx.xxxx, xxxx.xxxx)	(xxxx.xxxx, xxxx.xxxx)
	SD (log)	XXX.XXX	XXX.XXX
	Geometric %CV	XXX.X	XXX.X
AUC 0-<math>\infty</math> (h* $\mu$ g/mL)	n	xx	xx
	Mean (SD)	XXX.X (xx.xx)	XXX.X (xx.xx)
	95% CI	(xxxx.xx, xxxx.xx)	(xxxx.xx, xxxx.xx)
	%CV	xx.x	xx.x
	Median	XXX.XX	XXX.XX
	Min, Max	XXX.X, XXX.X	XXX.X, XXX.X
	Geometric mean	XXX.XX	XXX.XX
	95% CI	(xxxx.xxxx, xxxx.xxxx)	(xxxx.xxxx, xxxx.xxxx)
	SD (log)	XXX.XXX	XXX.XXX

Geometric %CV

xxx.x

xxx.x

/Directory/program.sas 01JAN2002 12:01

---

Programming notes:

- 1) Repeat table for RPV (Oral RPV 25mg, IM RPV 900mg; ng/mL, ng\*h/mL)
- 2) Repeat for all of the following PK parameters as available:  $C_{max}$ ,  $t_{max}$ ,  $t_{1/2}$ ,  $K_A$  LA,  $\lambda_z$ ,  $C_{24}$ ,  $C\tau$
- 3) For  $t_{max}$ , only the n, median, minimum, and maximum should be provided.
- 4) Report the means & median +1 decimal past the maximum length of results within parameter. Report the SD and 95% CI values +2 decimals past the maximum length of results within parameter. %CV statistics should be reported to 1 decimal.

**CONFIDENTIAL**

208832

Protocol: 208832  
Population: Screened

Page 1 of 1

HO 01  
Listing of CCI [REDACTED] Scores

Treatment	Site Id./ Unique Subject Id.	Treatment/ Injection Site Side	Visit	Date	CCI
Treatment A	PPD [REDACTED]	CAB/Left	Day 1 Day 2 Day 4 Day 5 Day 8	YYYY-MM-DDTHH:MM YYYY-MM-DDTHH:MM YYYY-MM-DDTHH:MM YYYY-MM-DDTHH:MM YYYY-MM-DDTHH:MM	[REDACTED]
		RPV/Right	Day 1	YYYY-MM-DDTHH:MM	[REDACTED]

USER ID:/PROGRAM PATH/PROGRAM DATE TIME

**CONFIDENTIAL**

208832

Protocol: 208832  
Population: Screened

Page 1 of 1

HO 02  
Listing of [REDACTED] Results at Day 8

[figure not shown]
Treatment: Treatment A

Site Id./ Unique Subject Id.	Date/Time of Assessment	Treatment/ Injection Site Side/ Domain	Question	Result
PPD	YYYY-MM-DD/ HH:MM	CAB/Left	CCI	[REDACTED]
...				
YYYY-MM-DD/ HH:MM				
CCI				

**CONFIDENTIAL**

208832

CCI

USER ID:/PROGRAM PATH/PROGRAM DATE TIME

**CONFIDENTIAL**

208832

Protocol: 208832

Population: Screened

Page 1 of 1

HO\_03  
Listing of Injection Area Symptoms from Daily Diary Cards

Treatment	Site Id./ Unique Subject Id.	Treatment/ Date of Injection		Assessment/ Study Day	Symptoms? (Y/N)	Pain (0-3)	Itching (0-3)	Other Symptoms [1]	Home Treatment [2]
		Site	Side						
Treatment A	PPD [REDACTED]	CAB/	Left	YYYY-MM-DD/ 1	Y	2	1	BU, SF	AP, Top
				YYYY-MM-DD/ 2	Y	0	1		Top
				...					
		RPV/	Right	YYYY-MM-DD/ 1	N				
				...					

[1] NO=None, BR=Bruising, BU=Bump, D=Discoloration, R=Redness, SF=Skin firmness, SW=Swelling, W=Warm to touch.  
[2] NO=None, AP=Acetaminophen/paracetamol (Tylenol), D=Diphenhydramine (Benadryl), Top=Topical anti-itch cream or ointment such as hydrocortisone/diphenhydramine, etc., W=Warm compress (heating pad), C=Cold compress (cold pack or ice pack).

USER ID:/PROGRAM PATH/PROGRAM DATE TIME

## 11.10. Appendix 10: AESI Identification

SMQ and PT codes based on MedDRA dictionary version 23.0.

### 11.10.1. Hepatotoxicity

SMQ: Hepatic failure, fibrosis and cirrhosis and other liver damage-related conditions SMQ Code: 20000013 Category: A Scope: Narrow	
Preferred Term	PT Code
Acquired hepatocerebral degeneration	10080860
Acute hepatic failure	10000804
Acute on chronic liver failure	10077305
Acute yellow liver atrophy	10070815
Ascites	10003445
Asterixis	10003547
Bacterascites	10068547
Biliary cirrhosis	10004659
Biliary fibrosis	10004664
Cardiohepatic syndrome	10082480
Cholestatic liver injury	10067969
Chronic hepatic failure	10057573
Coma hepatic	10010075
Cryptogenic cirrhosis	10063075
Diabetic hepatopathy	10071265
Drug-induced liver injury	10072268
Duodenal varices	10051010
Gallbladder varices	10072319
Gastric variceal injection	10076237
Gastric variceal ligation	10076238
Gastric varices	10051012

Gastric varices haemorrhage	10057572
Gastrooesophageal variceal haemorrhage prophylaxis	10066597
Hepatectomy	10061997
Hepatic atrophy	10019637
Hepatic calcification	10065274
Hepatic cirrhosis	10019641
Hepatic encephalopathy	10019660
Hepatic encephalopathy prophylaxis	10066599
Hepatic failure	10019663
Hepatic fibrosis	10019668
Hepatic hydrothorax	10067365
Hepatic infiltration eosinophilic	10064668
Hepatic lesion	10061998
Hepatic necrosis	10019692
Hepatic steato-fibrosis	10077215
Hepatic steatosis	10019708
Hepatitis fulminant	10019772
Hepatobiliary disease	10062000
Hepatocellular foamy cell syndrome	10053244
Hepatocellular injury	10019837
Hepatopulmonary syndrome	10052274
Hepatorenal failure	10019845
Hepatorenal syndrome	10019846
Hepatotoxicity	10019851
Immune-mediated cholangitis	10083406
Immune-mediated hepatic disorder	10083521
Intestinal varices	10071502
Intestinal varices haemorrhage	10078058
Liver dialysis	10076640

Liver disorder	10024670
Liver injury	10067125
Liver operation	10062040
Liver transplant	10024714
Lupoid hepatic cirrhosis	10025129
Minimal hepatic encephalopathy	10076204
Mixed liver injury	10066758
Nodular regenerative hyperplasia	10051081
Nonalcoholic fatty liver disease	10082249
Non-alcoholic steatohepatitis	10053219
Non-cirrhotic portal hypertension	10077259
Oedema due to hepatic disease	10049631
Oesophageal varices haemorrhage	10030210
Peripancreatic varices	10073215
Portal fibrosis	10074726
Portal hypertension	10036200
Portal hypertensive colopathy	10079446
Portal hypertensive enteropathy	10068923
Portal hypertensive gastropathy	10050897
Portal vein cavernous transformation	10073979
Portal vein dilatation	10073209
Portopulmonary hypertension	10067281
Primary biliary cholangitis	10080429
Regenerative siderotic hepatic nodule	10080679
Renal and liver transplant	10052279
Retrograde portal vein flow	10067338
Reye's syndrome	10039012
Reynold's syndrome	10070953
Splenic varices	10067823

Splenic varices haemorrhage	10068662
Steatohepatitis	10076331
Subacute hepatic failure	10056956
Sugiura procedure	10083010
Varices oesophageal	10056091
Varicose veins of abdominal wall	10072284
White nipple sign	10078438
SMQ: Hepatitis, non-infectious SMQ Code: 20000010 Category: A Scope: Narrow	
Preferred Term	PT Code
Acute graft versus host disease in liver	10066263
Allergic hepatitis	10071198
Alloimmune hepatitis	10080576
Autoimmune hepatitis	10003827
Chronic graft versus host disease in liver	10072160
Chronic hepatitis	10008909
Graft versus host disease in liver	10064676
Hepatitis	10019717
Hepatitis acute	10019727
Hepatitis cholestatic	10019754
Hepatitis chronic active	10019755
Hepatitis chronic persistent	10019759
Hepatitis fulminant	10019772
Hepatitis toxic	10019795
Immune-mediated hepatitis	10078962
Ischaemic hepatitis	10023025
Lupus hepatitis	10067737
Non-alcoholic steatohepatitis	10053219

Radiation hepatitis	10051015
Steatohepatitis	10076331

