### 2.3.1. Risk Assessment

Potential Risk of Clinical Significance	Summary of Data/Rationale for Risk	Mitigation Strategy
Drug Induced Liver Injury (DILI)	
A small proportion of participants in the CAB program to date (total exposure >3100 participants) have developed transaminitis (elevated liver transaminases characterized by predominant alanine aminotransferase (ALT) elevation). In most participants, transient transaminitis was explained by acute viral hepatitis infection (. In a small number of participants, there was not an alternative explanation, suggesting a mild form of drug induced liver injury (DILI) without hepatic dysfunction, which resolved upon withdrawal of treatment with CAB.
 
All participants with suspected DILI identified to date were receiving oral CAB.
	
 
Exclusion criteria as described in Section 5.2 will prohibit participation with significant liver impairment based on screening liver chemistry including transaminases (ALT and Aspartate aminotransferase [AST]) as well on prior medical history.
 
A 4-week oral lead-in Phase is being implemented in this study, where all participants will receive oral CAB prior to the administration of IM CAB to assess individual safety and tolerability. Liver transaminases (ALT and AST) will be monitored throughout this study (refer to Schedule of Activities) and the liver chemistry stopping criteria will be adopted as described in Section 7.1.1 of this protocol.
 
All instances of liver transaminase elevations of Grade 2 and above will be followed to resolution. Participants withdrawn from the study due to meeting liver chemistry stopping criteria will be regularly monitored both clinically and using liver chemistries to determine progress towards resolution of the liver event.
 

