### 11.3. Appendix 3: Adverse Events: Definitions and Procedures for Recording, Evaluating, Follow-up, and Reporting

#### 11.3.1. Definition of AE

AE Definition

• An AE is any untoward medical occurrence in a clinical study participant, temporally associated with the use of a study intervention, whether or not considered related to the study intervention.

• NOTE: An AE can therefore be any unfavorable and unintended sign (including an abnormal laboratory finding), symptom, or disease (new or exacerbated) temporally associated with the use of a study intervention.

Events Meeting the AE Definition

• Any abnormal laboratory test results (hematology, clinical chemistry, or urinalysis) or other safety assessments (e.g., ECG, radiological scans, vital signs measurements), including those that worsen from baseline, considered clinically significant in the medical and scientific judgment of the investigator (i.e., not related to progression of underlying disease).

 
Note: Clinically significant laboratory abnormalities captured as AEs should be graded as per the clinical AE grade criteria, rather than by laboratory grade to be graded by the central laboratory or central statistical analysis group using DAIDS laboratory grading criteria as per
 

• Exacerbation of a chronic or intermittent pre-existing condition including either an increase in frequency and/or intensity of the condition.

• New conditions detected or diagnosed after study intervention administration even though it may have been present before the start of the study.

• Signs, symptoms, or the clinical sequelae of a suspected drug-drug interaction.

• Signs, symptoms, or the clinical sequelae of a suspected overdose of either study intervention or a concomitant medication. Overdose per se will not be reported as an AE/SAE unless it is an intentional overdose taken with possible suicidal/self-harming intent. Such overdoses should be reported regardless of sequelae.

• The signs, symptoms, and/or clinical sequelae resulting from lack of efficacy will be reported as AE or SAE if they fulfill the definition of an AE or SAE. Also, "lack of efficacy" or "failure of expected pharmacological action" constitutes an AE or SAE.

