## 2.2.      Study Objective(s) and Endpoint(s)

**Table 2      Study Objectives and Endpoints**

Objectives	Endpoints
Primary Objectives	Primary Endpoints
• To describe the PK profiles of CAB and RPV following a single intramuscular injection each of CAB LA + RPV LA administered to the lateral thigh muscle in adult healthy participants.	• Maximum observed concentration ( $C_{max}$ ) and time of maximum observed concentration ( $t_{max}$ ) in plasma • Area under the concentration – time curve from time zero to last quantifiable time point ( $AUC_{0-t}$ ) through the follow-up phase • Area under the concentration – time curve from time zero to infinity ( $AUC_{0-\infty}$ ) • Apparent terminal phase half-life ( $t_{1/2}$ ) and absorption rate constant ( $K_A$ LA)

Safety Objectives	Safety Endpoints

 
To assess safety and tolerability of CAB and RPV following repeated oral dose and single intramuscular injection in the lateral thigh of healthy participants
 
	
 
Safety and tolerability parameters including adverse events (AEs), clinical laboratory tests, electrocardiogram (ECG), and vital sign assessments
 

Secondary Objectives	Secondary Endpoints

 
To assess liver safety and tolerability of CAB and RPV following repeated oral dose and single intramuscular injection in the lateral thigh of adult healthy participants
 
	
 
Tolerability parameters (liver related adverse events) and liver chemistry abnormalities
 

Exploratory Objectives	Exploratory Endpoints

CCI

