## **7.7. Other Safety Analyses**

Vital sign data (temperature, systolic and diastolic blood pressure, and pulse rate) will be summarized by study phase, visit, and planned time. Absolute values and change from baseline values will be shown. Injection phase Baseline will also serve as Follow-up phase Baseline. Vitals signs will be listed by subject, study phase, visit, planned time, and actual date and time.

Electrocardiogram (ECG) data including values and findings will be summarized by study phase, visit, and timepoint. Absolute values and change from baseline will be shown for PR, QRS, QT, QTcB, and QTcF results. Baseline will be calculated as the mean of triplicate readings recorded prior to first dose in each study phase.

All ECG data including clinical interpretation will be listed by subject, study phase, visit and record date. Clinically significant ECG abnormalities will be flagged and listed separately, and corresponding values will be provided.

Liver related adverse events and chemistry abnormalities will be summarized separately by study phase. See [Appendix 10](#) for a list of Hepatotoxicity AEs and [Appendix 7](#) for Chemistry values of Potential Clinical Importance.

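### The SAP 11.10.1 liver term list has no raised-enzyme, bilirubin or jaundice term, so an ALT event coded only to a laboratory term is left out of the liver-related AE summary (Table 3.24)

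*SAP*

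**What the plan says.** SAP Table 2 (section 2.2) gives a secondary liver-safety objective with a two-part endpoint: "Tolerability parameters (liver related adverse events) and liver chemistry abnormalities". SAP 7.7 summarises the two parts separately. For the AE part it says: "See [Appendix 10](#) for a list of Hepatotoxicity AEs". For the chemistry part it points to Appendix 7.

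The Appendix 10 list (SAP 11.10.1) has two blocks and no supplementary terms:

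- "SMQ: Hepatic failure, fibrosis and cirrhosis and other liver damage-related conditions SMQ Code: 20000013 Category: A Scope: Narrow"
- "SMQ: Hepatitis, non-infectious SMQ Code: 20000010 Category: A Scope: Narrow"

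The only liver-specific AE table in the SAP's list of displays is Table 3.24, the hepatotoxicity AESI summary.

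Protocol 2.3.1 describes the liver risk seen in the cabotegravir programme. A small proportion of participants "have developed transaminitis (elevated liver transaminases characterized by predominant alanine aminotransferase (ALT) elevation". Where no other cause was found, the protocol reads the cases as "suggesting a mild form of drug induced liver injury (DILI) without hepatic dysfunction". It adds that all suspected cases so far were in people taking oral cabotegravir, which participants here are scheduled to take for 28 days.

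Protocol 11.3.1 lists among the events that qualify as AEs "Any abnormal laboratory test results (hematology, clinical chemistry, or urinalysis) or other safety assessments", provided that the investigator judges the abnormality clinically significant.

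**The concern.** The list that defines the AE half of a stated secondary endpoint does not contain the terms under which the expected liver event may well be reported. A site that records a clinically significant ALT rise as a laboratory AE has followed Protocol 11.3.1, but the event has no matching term in SAP 11.10.1 and does not enter Table 3.24.

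At stake is the consistency of one summary. Two participants with the same liver event could be treated differently, one counted and one dropped, according to whether the investigator wrote a laboratory finding or a diagnosis. The liver-related AE summary could then show no events while other tables in the same report show one.

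**Working it through.** The plan states no figure to reproduce: Protocol 10.2 says there was no formal sample size or power calculation, and SAP section 7 plans no formal analysis of safety data. The check is a reading of the term list, a trace of the displays, and a small illustration of scale.

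**1. Term list.** Every preferred term in SAP 11.10.1 was transcribed.

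- First block: 86 terms. Second block: 20 terms. Total 86 + 20 = 106.
- Three terms are in both blocks (hepatitis fulminant, non-alcoholic steatohepatitis, steatohepatitis), so 106 − 3 = 103 distinct terms.
- Search for stems covering transaminases, ALT, AST, liver enzymes, function tests, bilirubin, jaundice, alkaline phosphatase, INR and prothrombin: 0 of 103 match.
- The list is not confined to diagnoses. At least 10 entries are procedures or prophylaxis (for example hepatectomy, liver transplant, Sugiura procedure), and some are signs (ascites, asterixis).
- Terms that would capture a transaminitis case recorded as a diagnosis are present: "Drug-induced liver injury", hepatocellular injury, liver injury, hepatotoxicity, hepatitis.

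**2. The same event under two wordings.**

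| Display | Recorded only as raised ALT | Recorded as drug-induced liver injury |
|---|---|---|
| Table 3.24, liver AESI summary | absent | counted |
| Tables 3.3 and 3.4, all AEs | counted | counted |
| Table 3.7, if judged drug-related | counted | counted |
| Table 3.12, if it led to discontinuation or withdrawal | counted | counted |
| Table 3.27, chemistry grade shifts | by laboratory value | by laboratory value |
| Tables 3.32 and 3.33, if their ALT-based criteria are met | by laboratory value | by laboratory value |

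Only the first row depends on the wording.

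**3. The other special-interest lists.** The seizure list (SAP 11.10.2) adds selected terms beyond its standard query. The QT list (SAP 11.10.3) contains an investigation term for a prolonged QT interval and adds one more from the ECG investigations group. The liver list has neither supplementary terms nor investigation terms, and no reason is given.

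**4. Scale, as illustration.** Protocol 10.2 plans about 15 injected participants. The denominator of Table 3.24 is the Safety population, meaning everyone who takes at least one dose (SAP Table 4). That number is not stated and may exceed 15. Exact (Clopper-Pearson) 95% limits:

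- 0/15: upper limit 1 − 0.025^(1/15) = 21.8%.
- 1/15 = 6.7%: lower limit 1 − 0.975^(1/15) = 0.2%; the upper limit solves (1 − p)^15 + 15p(1 − p)^14 = 0.025, which gives 31.9%.
- If 20 were dosed (assumed): 1/20 = 5.0%, and the upper limit for 0/20 is 1 − 0.025^(1/20) = 16.8%.

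The documents give no transaminitis rate. At assumed rates of 1%, 5% and 10%, the chance of at least one case among 15, 1 − (1 − p)^15, is 14%, 54% and 79%.

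**The case against.** The strongest answer is that the event is still reported. The secondary endpoint has a chemistry half, and ALT elevations enter it through Tables 3.27, 3.32 and 3.33 and Listings 32 and 33. The laboratory tables do not carry causality or seriousness, but the unfiltered AE tables and Listings 9, 11 and 13 do. A reader might infer from the gap in the list that transaminitis would go uncounted, or that a participant withdrawn in the oral lead-in for drug-related raised ALT would disappear from the report. The documents do not support that: such a participant would be in Tables 3.3, 3.4, 3.7 and 3.12. This part of the objection stands in full and confines the point to Table 3.24.

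Second, Protocol 11.3.3 asks for the diagnosis to be recorded in preference to signs and symptoms where possible, and the list holds suitable diagnoses. So it would be wrong to infer that every transaminitis case is missed. This stands too, but the rule applies only where a diagnosis can be made, so the count still turns on wording.

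Third, SAP 7.4 lets the terms change with safety review team agreements at reporting, and the current revision is labelled as critical components only. The list is therefore not final. Nothing there commits to adding laboratory terms, however, and adding them in an open-label study after the events are known is weaker than specifying them now.

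Fourth, restricting an AE list to narrow scope for specificity is a defensible choice. A separate subtotal preserves that specificity.

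**Conclusion.** The point holds in a limited form. SAP 11.10.1 has no raised-ALT, AST, transaminase, hepatic-enzyme, bilirubin or jaundice term, so an ALT-predominant AE coded only to a laboratory term is omitted from Table 3.24. The AE half of the secondary liver endpoint can then read zero while the laboratory tables and the unfiltered AE tables show the event. None of the objections puts the event back into that summary.

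The size is one participant per omitted event: at an assumed 15 participants, 6.7% becomes 0%. This cannot be turned into an expected effect, because the documents give neither a transaminitis rate nor the number dosed. It would also be a mistake to treat 15 as the true denominator, since it counts injected participants and someone who leaves during the oral lead-in is not among them. The conclusion assumes that Table 3.24 is where SAP 7.7's liver-related AEs are shown, as no other liver AE table is listed. No primary pharmacokinetic result or sample size is affected. This is a cheap improvement to a secondary safety summary.

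**What to change.** In the full RAP, which SAP 11.9 says is still to be developed:

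- Add a third block to SAP 11.10.1 with the liver-related investigation, bilirubin and jaundice preferred terms from the MedDRA version in use: raised ALT, AST, transaminases, hepatic enzymes and bilirubin, and jaundice.
- Show that block in Table 3.24 with its own subtotal.
- State in SAP 7.7 that liver-related AEs means all three blocks.
- Cross-reference Tables 3.27, 3.32 and 3.33 from Table 3.24.

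The cost is one block of terms, one sub-block in an existing table and a footnote. No new data are needed. The drawback is that some mild, non-specific enzyme AEs will be counted; the subtotal keeps them apart from the existing narrow-scope terms.

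If the sponsor prefers to keep the list as it is, the minimum is a sentence in SAP 7.7 saying that laboratory-coded liver AEs are excluded from Table 3.24, with the same cross-references.
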